5.1. Summary of Study Design

Study KFAJ is a multicenter, randomized, double-blind, placebo-controlled, parallel-group Phase 2 study to evaluate the efficacy and safety of LY3471851 in adult study participants with at least moderately active SLE. The study has 3 required study periods and an optional prescreening period. A schematic of the study design is presented in Figure 5.1.

Note: Visit 802 is for HBV DNA testing of randomized participants who were positive for antibody to hepatitis B core antigen (anti-HBc) at screening.

Abbreviations: anti-HBc = hepatitis B core antibody; FD = first dose administered; HBV = hepatitis B virus; LD = last dose administered; Q2W = every 2 weeks; V = eCRF visit; W = study week relative to baseline visit.

Figure 5.1. Schema of Study J1P-MC-KFAJ, a Phase 2 study to evaluate the efficacy and safety of LY3471851 in adults with systemic lupus erythematosus.

Optional prescreening period: The optional prescreening period is prior to Visit 1. The optional prescreening visit (Visit 601) is intended for those investigators who opt for central laboratory assessment of the prospective participant’s antinuclear antibodies, anti-double stranded DNA, and anti-Smith antibody status before full screening activities are initiated. The prescreening visit can be repeated 2 times (no more) per participant, with a minimum of 4 weeks between visits.

Screening period: The required screening period begins with Visit 1, which occurs within 5 weeks before the planned randomization visit (Week 0, Visit 2). Participants found to be eligible according to all of the study entry criteria will be randomly assigned in a 1:1:1:1 ratio to receive one of the following study interventions:

- **CCI** LY3471851 Q2W
- **CCI** LY3471851 Q2W
- **CCI** LY3471851 Q2W, and
- placebo Q2W.

Participants will be stratified at randomization according to disease activity at baseline, corticosteroid dose at baseline, and geographic region (Section 5.2). Study interventions will be administered via subcutaneous injection.

Double-blind treatment period: Randomized participants will begin the double-blind, placebo-controlled, 24-week treatment period at Visit 2. Participants will receive the first dose of the assigned study intervention at that visit and will continue to receive doses through the last scheduled dosing visit specified in protocol. Participants will maintain their usual standard-of-care medication regimen for SLE and for other diseases throughout the study, unless these medication regimens are specifically excluded by the study entry criteria. Safety and efficacy assessments and laboratory sample collections will be performed as specified in the protocol.

Follow-up period: All participants will have a posttreatment follow-up visit (Visit 801) for safety assessments. Randomized participants who were positive for anti-HBc at screening will have one additional posttreatment follow-up visit (Visit 802).

Early discontinuation: Participants who permanently discontinue the study drug early or withdraw from the study will undergo early termination procedures, including an ETV and the post-treatment follow-up visits specified in the protocol.

5.2. Method of Assignment to Treatment

Subjects who meet all criteria for enrollment will be randomized 1:1:1:1 to double-blind treatment at Visit 2. Participants will be stratified at randomization according to disease activity at baseline (SLEDAI-2K <10; SLEDAI-2K ≥10), corticosteroid dose at baseline (<10 mg/day or ≥10 mg/day), and geographic region. [Table KFAJ.5.1](#) describes how each region will be defined for the stratification at randomization as well as the statistical analyses and summaries.

Assignment to treatment groups will be determined by a computer-generated random sequence using an IWRS. The IWRS will be used to assign vials containing double-blind investigational product to each patient. Site personnel will confirm that they have located the correct vials by entering a confirmation number found on the vials into the IWRS. The IWRS will be used to assign investigational product to each patient. Site personnel will confirm that they have located the correct packages by entering a confirmation number found on packages into the IWRS.

Table KFAJ.5.1. Countries and Their Geographical Regions

Geographical Region	Country or Countries
North America	Canada, United States, Puerto Rico
Latin America	Argentina, Mexico
Europe	Belgium, Czech Republic, France, Germany, Hungary, Italy, Poland, Romania, Spain, United Kingdom
Asia	South Korea, Taiwan
Japan	Japan
Rest of World	Australia, India, Israel, Russia, Ukraine

6. A Priori Statistical Methods

6.1. Determination of Sample Size

CCI [REDACTED] will be randomly assigned to study intervention. All randomized participants in the mITT population as defined in Section 6.6 will be considered evaluable.

Pairwise 2-sided tests of proportions with $\alpha = 0.05$ will be performed on each LY3471851 dose versus placebo CCI [REDACTED], a placebo response of 0.40, and a LY3471851 response of 0.64 for the maximally efficacious LY3471851 dose, there is at least 80% power to detect a statistically-significant difference in SLEDAI-4 response between LY3471851 and placebo at Week 24 (Visit 15).

6.2. General Considerations

Statistical analysis of this study will be the responsibility of the sponsor or its designee. For primary and key secondary objectives, statistical analyses will be performed CCI [REDACTED] [REDACTED]

Not all displays described in this SAP will necessarily be included in the CSR. Not all displays will necessarily be created as a “static” display. Some may be incorporated into interactive display tools such as Spotfire instead of, or in addition to, a static display. Any display described in this SAP and not included in the CSR would be available upon request.

All tests of treatment effects will be conducted at a 2-sided alpha level of 0.05, unless otherwise stated. The p-values will be rounded up to 3 decimal places. For example, any p-value strictly >0.049 and ≤ 0.05 will be displayed as 0.050. This guarantees that on any printed statistical output, the unrounded p-value will always be less than or equal to the displayed p-value. A displayed p-value of 0.001 will always be understood to mean ≤ 0.001 . Likewise, any p-value displayed as 1.000 will be understood to mean >0.999 and ≤ 1 .

The primary analysis method for treatment comparisons of categorical efficacy and health outcome variables will be made using a logistic regression analysis with treatment group, baseline disease activity (SLEDAI-2K <10 ; SLEDAI-2K ≥ 10), corticosteroid dose at baseline (<10 mg/day or ≥ 10 mg/day), and geographic region (North America, Latin America, Europe, Asia, Japan, Rest of World) in the model. For each treatment comparison, an estimate of the treatment difference with corresponding Wald 95% CI, the odds ratio with corresponding Wald 95% CI and p-value will be presented. Each treatment group will be compared to the placebo group. The p-value for all other explanatory variables will also be presented. When logistic regression sample size requirements are not met (<5 subjects in any category for any factor), treatment comparison will be performed using the Fisher’s exact test.

The primary analyses for continuous efficacy and health outcome variables will be made using MMRM. When MMRM is used, the model will include treatment, baseline score, baseline disease activity (SLEDAI-2K <10 ; SLEDAI-2K ≥ 10), corticosteroid dose at baseline (<10 mg/day or ≥ 10 mg/day), geographic region (North America, Latin America, Europe, Asia, Japan, Rest of World), visit (as categorical variable), the interaction of treatment-by-visit, and

the interaction of baseline value-by-visit as fixed factors. An unstructured covariance matrix will be used to model the within-patient variance-covariance errors. If this analysis fails to converge, the following structures will be tested in this pre-specified order: 1) heterogeneous Toeplitz, 2) heterogeneous autoregressive, 3) heterogeneous compound symmetry, 4) Toeplitz, 5) autoregressive), and 6) compound symmetry. The first covariance structure that converges using this prespecified order will be used. The Kenward-Roger method will be used to estimate the degrees of freedom. Type III sums of squares for the LS means will be used for the statistical comparison. The LS mean for each treatment group along with the estimate of the difference between treatments (difference between each LY3471851 dose group and placebo), standard error, p-value, and the 95% CIs will be reported at each visit along with p-values. For variables that are not collected at each postbaseline visit, data may exist at visits where the variable was not scheduled to be collected, due to early discontinuation visits. In these situations, data from the early discontinuation visit that do not correspond to the planned collection schedule will be excluded from the MMRM analyses (Andersen and Millen 2013). However, the data will still be used in other analyses.

When ANCOVA is used for efficacy/Health Outcomes measures, the model will include treatment, baseline score, baseline disease activity (SLEDAI-2K <10 ; SLEDAI-2K ≥ 10), corticosteroid dose at baseline (<10 mg/day or ≥ 10 mg/day), and geographic region as fixed factors. Type III sums of squares will be used. Differences in LS means between treatment groups will be displayed, with the p-value associated with the LS mean comparison to placebo (for each LY3471851 dose group) along with the 95% CI of the LS mean difference also provided. In addition to the LS means and tests, mean, SD, minimum, first quartile, median, third quartile, and maximum will be displayed.

6.4. Definition of Baseline and Postbaseline Measures

Baseline will be defined as the last available value before the first dose of study drug for both efficacy and safety analyses, unless otherwise specified. In most cases, this will be the measure recorded at Week 0 (Visit 2). The treatment period starts after the first study drug administration and ends on one of the following:

- date of Visit 15 (Week 24) for patients who completed the treatment period
- for patients who discontinued treatment early
 - date of ETV, if ETV occurs less than 42 days after treatment discontinuation
 - date of the last visit that occurs less than 42 days after treatment discontinuation, if ETV occurs after 42 days since treatment discontinuation.

Change from baseline will be calculated as the visit value of interest minus the baseline value. Percent change from baseline will be calculated as 100 times change from baseline divided by baseline.

Postbaseline measurements are collected after study drug administration through Visit 15 (Week 24) or an early discontinuation visit. For electronic PROs related to efficacy assessments, unscheduled postbaseline visits that fall within the protocol-defined visit windows will be summarized in the by-visit analyses if there is no scheduled visit available. If more than 1 value is reported for the same scheduled visit, then the first value will be summarized in the by-visit analyses.

The Follow-up Period includes all visits that are 42 days or more after treatment discontinuation for patients who discontinue the treatment period early. For patients who complete the treatment period, the Follow-up Period includes Visit 801 for safety assessment. Randomized participants who were positive for anti-HBc at screening will have one additional posttreatment follow-up visit (Visit 802). The baseline value for the safety analysis of the posttreatment follow-up period is defined as the last nonmissing assessment prior to entering the posttreatment Follow-up Period, that is Week 24 (Visit 15) for treatment completers or last visit that occurred less than 42 days after treatment discontinuation for patients that discontinued treatment early. When the

Follow-up Period includes more than 1 visit, any safety analyses that are done for this period will only include the first visit of this period.

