Rating Scale; DNA = deoxyribonucleic acid; ECG = electrocardiogram; ETV = early termination visit; [CCI] [REDACTED]
[REDACTED]; HBV = hepatitis B virus; IL = interleukin; [CCI] [REDACTED]
[REDACTED] QIDS-SR16 = 16-Item Quick Inventory of Depressive Symptomatology–Self Report; [CCI] [REDACTED]
[REDACTED] SLE = systemic lupus erythematosus; SLEDAI-2K = Systemic Lupus Erythematosus Disease Activity Index
2000; [CCI] [REDACTED] V = visit; VAS = visual analog scale.

Post-treatment follow-up period of Study J1P-MC-KFAJ			
Visit 802 is only for randomized participants who were positive for anti-HBc at screening. All other participants will complete the study at V801.			
Visit number	V801	V802	Comment
Weeks from randomization	30 or ETV + 6 to 8 weeks (to ensure 8 weeks from last dose)	38 or ETV + 14 to 16 weeks (to ensure 16 weeks from last dose)	Visit 801 occurs at Week 30, 8 weeks after the last dosing visit at Week 22 for patients who complete the study. If required, Visit 802 occurs at Week 38, 16 weeks after the last dosing visit at Week 22 for patients who complete the study. For patients who terminate early, the interval between ETV and the post-treatment follow-up visit(s) should be adequate to ensure that 8 weeks have elapsed since last dose for Visit 801 and 16 weeks have elapsed since last dose for Visit 802.
Study day	211	267	
Visit interval tolerance (days)	±7	±7	
Fasting visit			No fasting in this period.
Concomitant medications	X	X	
Adverse events (AEs)	X	X	CCI [REDACTED]
Physical Evaluation			
Weight	X		
Vital signs	X	X	Blood pressure, body temperature, and pulse rate. Vital signs should be measured after participant has been sitting for at least 5 minutes.
Injection site assessment	X		Performed by independent injection site assessor before participant is seen by blinded site staff (Section 6.3, Section 8.2.11).
Symptom-directed physical examination	X	X	See Section 8.2.2.
Clinician-Administered Questionnaires (Paper)			
C-SSRS Since Last Visit	X	X	Adapted for the assessment of ideation and behavior categories only.
Self-Harm Supplement Form	X	X	
Self-Harm Follow-Up Form	X	X	Required if triggered by Self-Harm Supplement Form, per instructions.

Post-treatment follow-up period of Study J1P-MC-KFAJ			
Visit 802 is only for randomized participants who were positive for anti-HBc at screening. All other participants will complete the study at V801.			
Visit number	V801	V802	Comment

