9.4. Statistical Analyses

9.4.1. General Considerations

CCI Unless other indicated in the SAP, the analyses will be conducted as follows:

- Primary and secondary endpoint analyses will be tested at a 2-sided α level of 0.05 for frequentist analyses.
- The primary estimand that will be used to analyze primary and secondary endpoints is a composite response estimand where comparisons will not include data collected after

intercurrent events of changes to background therapies or discontinuation. Participants who discontinue treatment prior to 24 weeks or who are noncompliant with concomitant medication rules are defined as nonresponders. Endpoint definition effectively gives complete data which will be analyzed as described in Section 9.4.2 and Section 9.4.3.

- No adjustments for multiplicity will be performed.
- Efficacy and PRO analysis models may contain the independent variables such as treatment group, baseline disease activity, and geographic region.
- Missing data for dichotomous responder endpoints will be imputed using the nonresponder imputation (NRI) method.
- Participants will be considered nonresponders for the NRI analysis if
 - they do not meet all the clinical response criteria
 - they are noncompliant with concomitant medication rules (Section 6.5)
 - they permanently discontinue study intervention at any time before the end of the treatment period for any reason, or
 - they are randomized and do not have at least 1 postbaseline observation.
- Mixed-effects model for repeated measures (MMRM) is the main method for analyzing continuous efficacy endpoints.
- Additional imputation methods may be considered for all endpoint types.

Baseline will be defined as the last available value before the first dose of study intervention for both efficacy and safety analyses. In most cases, this value will be what is recorded at the randomization visit (Visit 2). Change from baseline will be calculated as the visit value of interest minus the baseline value. For the post-treatment Follow-up Period, the baseline is defined as the last nonmissing assessment on or prior to entering the post-treatment Follow-up Period, that is, on or prior to the Week 24 visit, or the early termination visit (including ETV).

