- Box plots for observed values: Values at each visit (starting at randomization) and change from baseline to each visit and to last postbaseline measure will be displayed in box plots for patients who have a baseline and at least 1 postbaseline visit. For visits included in the treatment period, patients will be included only if the visit occurs on or before the date of treatment discontinuation/completion. Follow-up visit will be the first visit that occurred during the Follow-up period. Individual measurements outside of reference limits will also be displayed using distinct symbols overlaying the box plot. Original-scale data will be used for the display but for some analytes (for example, immunoglobulins) a logarithmic scale will be used to aid in viewing the measures of central tendency and dispersion. Unplanned measurements will be excluded. Descriptive summary statistics will be included in a table below the box plot. These box plots will be used to evaluate trends over time and to assess a potential impact of outliers on central tendency summaries. A p-value for change from baseline to endpoint will be provided using an ANCOVA model with explanatory term for treatment and the baseline value as a covariate. Endpoint will be the last observation where patient is on treatment.
- Treatment-emergent high/low analyses: the number and percentage of patients with treatment-emergent high and low laboratory results at any time will be summarized by treatment group. Planned and unplanned measurements will be included. A treatment-emergent **high** result is defined as a change from a value less than or equal to the high limit at all baseline visits to a value greater than the high limit at any time during the treatment period and up to 60 days after treatment discontinuation. A treatment-emergent **low** result is defined as a change from a value greater than or equal to the low limit at all baseline visits to a value less than the low limit at any time during the treatment period and up to 60 days after treatment discontinuation. The Fisher's exact test will be used for the treatment comparisons.

A listing of abnormal findings will be provided. The listing will include, but not be limited to, patient ID, treatment group, laboratory collection date, analyte name, and analyte finding.

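### SAP 6.4 can leave an in-window Visit 801 of an early discontinuer in neither the treatment nor the follow-up period, depending on an undefined discontinuation date, and its follow-up baseline differs from Protocol 9.4.1

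*SAP*

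**What the plan says.** SAP 6.4 sets the periods for early discontinuers by counting days from treatment discontinuation. The treatment period ends on the "date of ETV, if ETV occurs less than 42 days after treatment discontinuation"; a second bullet handles an ETV later than that by going back to the last visit before day 42. Follow-up begins separately: "The Follow-up Period includes all visits that are 42 days or more after treatment discontinuation for patients who discontinue the treatment period early". The baseline for follow-up safety analyses is the "last visit that occurred less than 42 days after treatment discontinuation for patients that discontinued treatment early". Where follow-up holds more than one visit, only the first is analysed. For completers the SAP assigns Visit 801 to follow-up by visit number, with no day count.

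Protocol 1.3 schedules Visit 801 at week "30 or ETV + 6 to 8 weeks (to ensure 8 weeks from last dose"), with "Visit interval tolerance (days) ±7 ±7" for Visits 801 and 802. Only anti-HBc-positive participants have Visit 802.

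Protocol 9.4.1 defines the follow-up baseline differently, as the last nonmissing assessment "on or prior to the Week 24 visit, or the early termination visit (including ETV").

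For the laboratory box plots, SAP 6.19.5 adds: "Follow-up visit will be the first visit that occurred during the Follow-up period".

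**The concern.** The treatment period stops at one event (the ETV), and follow-up starts at a day count from another (treatment discontinuation). Nothing in SAP 6.4 makes the two meet. A visit after the ETV but before day 42 is in neither period, although it satisfies the SAP's definition of the follow-up baseline. The 42-day cut equals the nominal interval from the end-of-treatment visit to Visit 801, so a Visit 801 held slightly early within its tolerance is the visit at risk.

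At stake are displays restricted to the treatment and follow-up periods with no extra window: the myelosuppression grades and shift tables (SAP 6.19.5.2), categorical vital signs (SAP 6.19.6) and the follow-up visit in the box plots (SAP 6.19.5). Haematology and vital signs are collected at Visit 801, and several haematology results are reasons for permanent discontinuation (Protocol 7.1.1), so some participants for whom recovery matters could be missing from those tables.

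**Working it through.** **Inputs.** Last dose at Week 22, Visit 15 at Week 24, Visit 801 at Week 30, tolerance ±7 days, 8 weeks (56 days) since last dose (all Protocol 1.3); 42-day cut (SAP 6.4).

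**Reproducing the schedule for completers.** Last dose day = 1 + 22×7 = 155. Visit 15 day = 1 + 24×7 = 169. Visit 801 day = 1 + 30×7 = 211. So Visit 801 is 211 − 155 = 56 days after last dose and 211 − 169 = 42 days after Visit 15, which agrees with the schedule.

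**Early discontinuers.** Let d = days from last dose to ETV. The Visit 801 target is ETV + max(42, 56 − d). The earliest allowed date depends on whether the full −7 days applies, or whether 56 days since last dose is a floor that the tolerance cannot breach. The protocol text supports either reading.

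| d | Target | Earliest, full −7 days | Earliest, 56-day floor kept |
|---|---|---|---|
| 0 | ETV + 56 | ETV + 49 | ETV + 56 |
| 7 | ETV + 49 | ETV + 42 | ETV + 49 |
| 8 | ETV + 48 | ETV + 41 | ETV + 48 |
| 14 | ETV + 42 | ETV + 35 | ETV + 42 |
| 15 | ETV + 42 | ETV + 35 | ETV + 41 |
| 21 | ETV + 42 | ETV + 35 | ETV + 35 |

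**Comparison with the 42-day cut.**
- Discontinuation dated at the ETV: Visit 801 can fall before day 42 when d ≥ 8 (full tolerance) or d ≥ 15 (floor kept).
- Discontinuation dated k days before the ETV: a Visit 801 at ETV + 35 is on day 35 + k, which is below 42 only if k < 7.
- Discontinuation dated at last dose: the earliest Visit 801 is day 49 (full tolerance) or day 56 (floor kept), so it does not fall in the gap.

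**Size.** The documents give no distribution of d or of visit dates. As an illustration, assume discontinuation is dated at the ETV, the full tolerance applies, visit dates spread evenly over the 15-day window, and d is even over 0 to 14. The number of window days below 42 is d − 7 for d = 8 to 14 and zero otherwise. The share is (1+2+…+7)/(15×15) = 28/225 = 12.4% of early discontinuers. With the 56-day floor kept, the share over the same range of d is zero.

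**Baseline.** A Visit 801 in the gap can serve as baseline only if a later visit exists, in practice Visit 802. The conflict with Protocol 9.4.1 does not depend on Visit 801: an unscheduled visit after the ETV and before day 42 qualifies under the SAP and not under the protocol, whichever date is meant. Such visits are to be expected, since Protocol 8.2.5 and 8.2.9 call for repeat tests after abnormal results.

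**Boundary.** The first treatment-period bullet covers an ETV before day 42 and the second an ETV after it. An ETV on exactly day 42 meets neither.

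**The case against.** The strongest reply is that the gap rests on one reading of an undefined date. SAP 6.4 has separate rules for ETVs before and after day 42, so it evidently treats discontinuation as distinct from the ETV and possibly well before it. If it means last dose, Visit 801 is safe. This stands as a condition on the point. The contrary evidence favours a date other than last dose without settling it. SAP 6.19.1 names last dose and discontinuation as alternatives. SAP 6.19.5 keeps treatment-period laboratory visits only up to the discontinuation or completion date; for completers that cannot be last dose (day 155), or the Visit 15 samples (day 169) would be excluded.

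A reader might infer a much larger effect. At d = 14 with the full tolerance, 7 of 15 window days (47%) lie below the cut. Multiplied by an assumed 10–20% early discontinuation, that gives 4.7–9.3% of participants. The documents do not support this. It applies the d = 14 fraction to every discontinuer, and at d = 14 a visit on ETV + 35 is only 49 days after last dose, which fails the 8-week condition if that is strict. The 12.4% average with the same assumed rates gives 1.2–2.5%. No discontinuation rate is stated; Protocol 7 calls permanent discontinuation rare and Protocol 7.2 expects withdrawal to be uncommon.

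A reader might also infer that recovery after stopping could not be assessed at all. That goes too far. Treatment-emergent laboratory results, the abnormal hepatic summaries (by their lead sentence) and the QIDS-SR16 shift tables run to 60 days after discontinuation and so include days 35–41. Abnormal laboratory findings and all adverse events are listed.

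Finally, counting days for irregular discontinuation visits is defensible, and handling completers by visit number is not in itself an inconsistency. Assigning follow-up by visit number alone would leave an ETV later than day 42 in no period. That is correct, and the fix below allows for it.

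**Conclusion.** The point holds conditionally and is minor. If treatment discontinuation is dated at the ETV or less than 7 days before it, SAP 6.4 can place a protocol-compliant Visit 801 in neither period. If 8 weeks since last dose is a strict floor, this also needs an ETV at least 15 days after last dose. If the date means last dose, Visit 801 is unaffected.

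The number affected cannot be derived from the documents and is probably small; the 12% of early discontinuers is an illustration resting on the assumptions shown. The use of Visit 801 as follow-up baseline is confined in practice to anti-HBc-positive participants with a Visit 802. Others simply have no visit left in the follow-up displays. Efficacy analyses and the 60-day-window safety analyses are untouched.

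Two defects do not depend on how the date is read: the follow-up baseline differs between SAP 6.4 and Protocol 9.4.1, and an ETV on exactly day 42 has no treatment-period rule.

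**What to change.** In SAP 6.4:

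1. Define the treatment discontinuation date.
2. Reword the second treatment-period bullet so that it covers an ETV at 42 days or more, which closes the day-42 boundary.
3. Define the Follow-up Period of early discontinuers as all visits after the end of the treatment period. Visits 801 and 802 then always count, whatever the day count, and an ETV at day 42 or later also falls in follow-up.
4. Define the follow-up baseline as the last nonmissing value on or before the end of the treatment period. In the usual case this is the ETV, consistent with Protocol 9.4.1. State the late-ETV case as an explicit exception to the protocol wording.
5. As a consequence of item 3, say which visit the first-visit rule selects when an unscheduled visit or a late ETV precedes Visit 801.

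The cost is SAP wording and a small change to the period derivation. No new data are needed, and items 2 to 4 work whichever date is chosen in item 1.
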